#### 9.2.2 Assessment of secondary outcomes

The secondary outcome is the comparison of the two hearing results. The IMD combines an automated screening into the hearing aid fitting. The results from this screening will be compared with a standard audiometry test performed by the investigator. This will be measured at the first visit.

Additionally, the data recording from the hearing aids will be compared including the average amount of time in hours per day that the hearing aids are worn and in which listening environments: quiet, speech in quiet, speech in noise, and noise. This information will be collected at the end of each field trial period when the subjects return to the clinic.

#### 9.2.3 Assessment of other outcomes of interest

Other outcomes of interest include speech testing as an objective measure of the hearing aids programmed with the IMD and the RMD. The Freiburger Sprachverständnistest consists of speech material that contains groups of 10 multi-syllable words which are numbers. The words are presented every 5 seconds. The participant must repeat the word immediately after they hear it. The goal is to find the presentation level at which the participant can repeat approximately 50% of the words correctly. This level will be measured for the unaided and aided conditions and recorded as test outcomes by the investigator. The differences between unaided and aided (IMD vs. RMD) will be used as an explanatory variable for the model.

Also, the perceived handicap associated with hearing impairment could potentially play a role in the perceived benefit from hearing aid. The Gothenburg Profile (GP) is a 20-item questionnaire with a 5 points scale (how often...? never, rarely, sometimes, often, and always). It will be given to the subjects on their first visit.

#### 9.2.4 Assessment of safety outcomes

During the use of the IMD the subjects will be asked to alert the investigator to any unexpected or uncomfortable sounds heard during the screening or the fitting of the hearing aid.

Additionally, they will be asked about any adverse events or unexpected events that involve the hearing aids. Unexpected events or effects include feedback or whistling from the device, unexpected sounds or artefacts from the device, discomfort, muting or shutting off of the device in mid-use, unexplained warning signals or beeping from the device, loud sounds, and occlusion. The information provided from the field trial will alert the testers to the potential for safety risks that should be addressed before the product is released to the market. It is not expected that any of these things will occur and have not during testing on previous products.

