Objective(s):	The purpose of this research is to determine the potential of a narrative influence on the subjective benefit of the hearing instruments with the traditional fitting method versus the self-directed method. Furthermore, the objective benefit of the hearing instruments should not be affected by using a different fitting method. The gain applied by each fitting method should be the same and will be controlled by electro-acoustical measures.	

Outcom e(s):	Primary Endpoint:			
	
 
Primary Outcome is the subjective benefit with the standard fitting compared to the self-directed fitting (using questionnaires)
 
			
	Secondary Endpoints:			
	
 
Audiometry will be compared using the standard measurement made by the Investigator as a control against the self-directed measurement
 
			
	Comparison of the objective performance of the devices (using speech testing)			
	
 
Procedural safety meaning that there are no unwanted noises or artefacts heard from the devices (as reported by the subjects)
 
			
	
 
Scores from speech tests and questionnaires will be compared between the self-directed fitting and the standard fitting method.
 
			
	
 
No unexpected, unwanted behavior of the devices or unexpected device related AEs or SAEs.
 
			
Study design :	This is a controlled, randomized, cross-over, open label, comparative clinical investigation conducted at two sites within the canton of Bern.			
	The study is based on a population of hearing impaired people that have hearing loss appropriate for the tested devices.			
	The treatment assignment of participants is randomized as well as the test condition order during the lab testing.			
	The standard fitting method will be used as a control. The hearing instruments will be exactly the same.			
	There is no placebo or "fake" device that does not provide amplification. A randomized cross-over design is used with half of the test subjects wearing the device fit with the traditional fitting method first and the other half using the self-directed method and then switching after approximately $10 + -5$ days.			
	A lab test will be used to test speech in a simulated environment. After each field trial period, the participants will be tested unaided and aided with speech material.			

Inclusion / Exclusion	Inclusion Criteria:
criteria:	All types of hearing loss (sensorineural, conductive, mixed)

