### 5.4 Safety Outcomes

The test participants will be asked whether anything unexpected that occurs during the field trial periods. Unexpected things include feedback or whistling from the device, unexpected sounds or artefacts from the device, discomfort, muting or shutting off of the device in mid-use, unexplained warning signals or beeping from the device, loud sounds, and occlusion. The information provided from the field trial will alert Bernafon to the potential for safety risks that should be addressed before the product is released to the market.

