#### 8.2.2 Control Intervention

The hearing screening results achieved from the IMD will be manually entered into the standard Oasis software for the fitting with the RMD. The hearing aids will be connected to the software using the same wireless neck loop used for the programming with the IMD. The investigator will fit the hearing aids and then place them in the subject's ears.

The subject will then wear the hearing aids for 10 days. The device will be inserted into the ear and placed over the ear each morning by the subjects themselves and removed each night by the subjects themselves. There is minimal training needed for a first time user to learn how to insert a hearing device. The subjects will be given an Instructions for Use booklet that explains how to insert the device and provides further instructions concerning cleaning, battery changing, and warnings.

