### 11.1 Hypothesis

Both devices will have the same electro-acoustical performance; however, it is suspected that changing the fitting procedure might influence the subjective benefit for the hearing aid user. Research suggests that placebo effect might impact hearing aid trials (Dawes et al., 2013) and that clinician behavior might also modify the perceived benefit of hearing aids (Naylor et al., 2015). The designed test will investigate the potential effect of the IMD compared to the RMD on first time users.

The test should answer the following research questions:

- Narrative effect of fitting procedure: Do different fitting procedures lead to differences in perceived benefit with hearing aids despite similar electro-acoustical performance? (Questionnaires)
- 2. Self-administrated audiometry: Is AMTAS self-administrated screening equivalent to standard clinical procedure? (hearing loss thresholds)

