3.1 Sample size proposal

Sample size cannot be computed on reported effect sizes from previous experiment, however, the following summary shall be used as an indication to determine the sample size for participants per investigator:

- Naylor et al. (2015) about the narrative effect during the fitting with 24 experienced users and 16 first time users. 83% of the experienced HA users had a preference for a given fitting method and 87.5 % for the first time users. Test design was repeated measures and separate analysis on groups based on experience.
- Dawes et al. (2011) about the placebo effect in hearing aid trials with 20 experienced hearing aid users.
 75% of the listeners had a preference for the labelled "new" hearing aid (effect size = 0.50),
- Dawes et al. (2013) about the placebo effect in hearing aid trials with 16 experienced hearing aid users. 75% of the listeners had a preference for the labelled "new" hearing aid (effect size = 0.66),
- Humes et al. (2017) about the performances with over the counter hearing aids compared to audiology best practice with 154 participants. Between groups test design with 3 arms (placebo, reference device, and over the counter alternative).

Placebo effect was found with sample sizes about 20 participants in single site study design. Adding an investigator effect in the design might bring new insights in this domain but need to have a minimum participant per investigator to reduce imbalance between them. A minimum of 24 participants will be included in the test with 4investigators and at least 6 participants per investigator.

This number is in line with Naylor et al. (2015) proposal who wanted "to compare the effect sizes generated by the experimental contrast in this study with those generated in typical studies of alternative HA systems, so we chose a sample size (n = 24) commensurate with such studies. Approximately 75% of studies comparing alternative HA systems utilize $n \le 25$ (Naylor 2005). Statistical power calculations based on HHIE data from another study of a non-acoustical intervention (Thorén et al. 2014) indicate that n = 18 would be sufficient to detect a 10-point change in HHIE score in either direction with an alpha of 0.05 and a Power of 0.8."

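### Section 9.2.4 asks participants to report unexpected sounds in the clinic only while the IMD is in use; the same request should be made at the RMD fitting

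*Protocol*

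**What the plan says.** Protocol 9.2.4 contains two enquiries.

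- The first takes place in the clinic and is worded for one method: "During the use of the IMD the subjects will be asked to alert the investigator to any unexpected or uncomfortable sounds". The sentence then confines this to two steps, the screening and the fitting.
- The second follows directly and is not limited to a method: "Additionally, they will be asked about any adverse events or unexpected events that involve the hearing aids". Its list of examples includes whistling, artefacts, beeping and loud sounds.

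Protocol 5.4 applies the second kind of enquiry to both wearing periods: "The test participants will be asked whether anything unexpected that occurs during the field trial periods". The synopsis makes the matter a secondary endpoint: "Procedural safety meaning that there are no unwanted noises or artefacts heard from the devices (as reported by the subjects").

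For the RMD, 8.2.2 describes manual entry of the screening results, connection through the same neck loop, and then: "The investigator will fit the hearing aids and then place them in the subject's ears". It mentions no request about sounds. Sections 9.3.1 and 9.3.2, which set out Visits 1 and 2, mention none either.

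**The concern.** The plan works hard to make the fitting procedure the only difference between the two periods. Both fittings use the IMD screening results, fine tuning is barred, and participants are not told that the aids are programmed alike. Section 11.1 gives the reason: earlier work suggests that "clinician behavior might also modify the perceived benefit of hearing aids". A clinician's request to listen for troublesome sounds, made at one kind of fitting and not at the other, is itself clinician behaviour. It appears in the safety section and not in the description of the self-directed procedure (8.1.1, 8.2.1), so it belongs to the trial and not to the product under test.

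Two things are at stake. Part of any IMD-RMD difference on the IOI-HA, the product questionnaire or the preference form could come from the trial's instructions and not from self-directed fitting. In addition, a sound heard at an IMD fitting is more likely to be reported on the spot than the same sound at an RMD fitting, although unwanted IMD behaviour is named in 4.2 as a second primary objective.

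**Working it through.** The question is mainly one of setting the texts side by side. The one relevant calculation is a check on whether any stated figure depends on the point.

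**1. Where the in-clinic request falls.** Everyone uses the IMD for audiometry at Visit 1 (footnote to the study schedule). The fitting then depends on the sequence.

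| Step | IMD first | RMD first |
|---|---|---|
| Visit 1, IMD screening | request | request |
| Visit 1, fitting | IMD: request | RMD: none stated |
| Visit 2, fitting | RMD: none stated | IMD: request |

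The screening row is the same in both sequences. At the fitting step the request goes with 2 of 2 IMD fittings and 0 of 2 RMD fittings. It therefore follows the method and not the period, so the cross-over does not cancel it and the analysis cannot separate it from the method.

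**2. What is asked for both methods.**

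- The second enquiry in 9.2.4, applied by 5.4 to the field periods (one IMD and one RMD period per participant).
- Verbal reports of sounds from the hearing aids (synopsis).
- A diary, and adverse event collection at every visit (10.1).
- An adverse event definition that covers both devices and the procedures (10.1.1).

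The asymmetry is therefore confined to real-time reporting at the fitting.

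**3. Whether the reports can be told apart.** The list of CRF contents in 12.1.1 has fields for adverse events and device effects, but none for sounds reported in the clinic. As listed, reports from the screening, the IMD fitting and the RMD fitting would have no separate place.

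**4. Whether any stated figure changes.** The power statement is for the chi-squared preference test, with noncentrality N × w².

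- Three outcomes (Protocol 11.2, SAP 3.2): 24 × 0.65² = 10.14, 2 degrees of freedom, alpha 0.05. Power is 0.821, against 0.82 stated.
- Two outcomes (SAP 3.2): 24 × 0.6² = 8.64, 1 degree of freedom. Power is 0.836, against 0.84 stated.

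Both reproduce, and neither involves the safety enquiry.

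**5. Whether the size can be computed.** It cannot. The documents give no rate of unwanted sounds and no effect of a reporting request. The nearest evidence is indirect. SAP 3.1 reports for each of two placebo studies that "75% of the listeners had a preference for the labelled" new aid, but these were experienced users and the label was favourable. SAP 2.1 reports a non-significant 0.5 points on the IOI-HA (maximum 35) between the preferred and less preferred fitting in 16 first-time users, the population of this trial. The first shows that words can move preference. The second cautions against assuming a large effect here.

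**The case against.** The other side has a good case, and much of it stands.

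- **The endpoint has RMD data.** A reader of the first sentence of 9.2.4 might infer that unwanted sounds are asked about for the IMD alone, and that the endpoint has no RMD comparator. The next paragraph of that section, with 5.4, 10.1 and 10.1.1, rules this out. Adverse event enquiry also follows each fitting, at the next visit. Only the prompt at the RMD fitting itself is missing.
- **No comparison of fitting sounds is planned.** The synopsis endpoint is absolute, and 11.4.6 rests on reported adverse events and clinical judgement. Extra attention to software without a CE mark is reasonable. This stands as a defence of asking during IMD use. It does not explain why the RMD fitting should go without the request.
- **Much of the exposure is shared.** Every participant meets the request at the IMD screening, and RMD-first participants meet it just before their RMD fitting at the same visit. This weakens the contrast. What remains is the IMD fitting step, which 8.2.1 limits to 20 minutes. It does not vanish, because in an open-label trial the screening request is still visibly tied to the IMD.
- **It is a request and not a prediction.** One might read the sentence as telling participants to expect odd sounds. It asks them to report any that occur, which is milder.
- **The 75% figures do not size it.** They concern a deliberately favourable label, and SAP 3.1 does not state that the aids compared were acoustically identical. They support plausibility only.

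**Conclusion.** The point holds at the fitting step. The in-clinic request is written for the IMD only, so an open-label trial of a fitting-procedure effect carries an instruction of its own on one side of the primary contrast, and sounds at the fitting are not ascertained equally. The size is unknown and possibly small, and no stated number changes.

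It would go too far to conclude that the primary comparison is shown to be confounded. An effect of the request on ratings is a plausible inference that the documents neither state nor quantify.

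The verdict assumes that investigators follow the text as written. If in practice they ask at both fittings, the difference disappears, but nothing in the protocol tells them to. The point is a cheap improvement and not a flaw that threatens the trial.

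**What to change.** In 9.2.4, keep the request during the IMD screening, and state that the same neutrally worded request is made at every fitting, IMD and RMD, at Visits 1 and 2. Simply replacing the reference to IMD use with a reference to fittings would drop the prompt from the screening, so both must be named. Carry the sentence into 8.2.1, 8.2.2, 9.3.1 and 9.3.2.

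Record the answer (yes or no, with a description) separately for the IMD screening, the IMD fitting and the RMD fitting. In the report, tabulate these apart from the field-period reports. The two fitting counts can then be set side by side, while the screening count stays descriptive because it has no step of its own on the RMD side.

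The cost is a short amendment to the text, a script and one CRF line. It needs no extra visit or procedure, and no safety information is lost.

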#### 9.2.4.1 Adverse events

For the recording of adverse events the subjects will be asked for a description of the event including how long it lasted, how many times it occurred, and if it caused discomfort or pain or a disruption of hearing ability. They will be recorded on the AE forms in the CRF.

9.2.4.2 Laboratory parameters Not applicable

9.2.4.3 Vital signs Not applicable

[figure not shown]
#### 9.2.5 Assessments in participants who prematurely stop the study

After the study concludes the subjects will return the hearing aids. They will have the choice of purchasing hearing aids and continuing a regular follow-up procedure with the clinic that recruited them. Those that withdraw prematurely will also have the option to purchase hearing aids and continue with normal follow-ups as needed with the clinic that recruited them.

### 9.3 Procedures at each visit

#### Visits to Clinic

#### 9.3.1 Screening Visit/First Visit

Screening visit, Day 0: The trial will be explained including how many visits are expected as well as the type of testing that they will complete. They will be given the Patient Information sheet and everything explained to them by the site investigator. Subjects are given time during the appointment to decide, whether or not to participate in the study. If they choose to not take part in the trial they will not sign the consent form and the appointment will finish. They can still follow-up with the clinic for a standard hearing aid purchase if they choose. If they choose to join the trial they will sign and date the Patient Informed consent form. No trial activities will be performed before the Patient Informed consent form is signed and dated by the subject and investigator. Subjects will receive a copy of the signed patient informed consent form and the patient information. A hearing history is then taken and otoscopy is performed. The initial hearing test is performed to determine hearing loss including air and bone audiometry. Inclusion/exclusion criteria will be determined. The subjects will then complete a questionnaire to quantify their perceived hearing loss handicap (Gothenburg). They will complete a hearing screening using the IMD. Based on the randomization plan they will be fitted with hearing aids either with the IMD or the RMD. The investigator will make no fine tuning of the fittings. Gain and features will be set as prescribed by the software. They will receive an Instructions for Use (IFU) for the They will be given a standardized questionnaire (IOI-HA) and a custom product hearing aid. questionnaire to fill out during the first period of the field trial. The HCP will review the questionnaires to ensure that the subjects understand their task. They will be scheduled for the Second Visit. Any AEs will be reported in the CRFs.

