# STUDY SCHEDULE

Study Periods	Intervention Period		I
Visit	Screening/1	2	3
Day	0	10 +/- 5 days	20 +/- 5 days
Patient Information and Consent	х		
Demographics	Х		
Medical/Hearing History	Х		
In-/Exclusion Criteria	Х		
Randomization	х	x	
Otoscopy	Х	х	х
Audiometry	Х		
Administer Medical Device	X*	X*	
Baseline Measure (Gothenburg questionnaire)	x		
Primary Variable (IOI-HA questionnaires)	x	x	
Secondary Variables (audiometry)	х		
Other Variables (speech testing)		x	x
Other Variables (product questionnaire)	х	x	
Other Variables (preference questionnaire)			x
Adverse Events	х	х	x

\*Depending on randomization subjects will be fit with IMD at the first or second visit. Everyone will use the IMD at the first visit to perform audiometry.

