### 7.3 Assignment to study group s

The participants are randomized by a block assignment as they appear at the trial sites. There will be 24-40 subjects. The test condition order will be randomized using a 2-factor randomization with a 6 block design. The first factor is the investigator with 4 levels, and the second factor is the test order with 2 levels. This will minimize the bias created when one test condition is tested in the first or last position all of the time.

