### 8.2 Admini stration of experimental and control interventions

#### 8.2.1 Experimental Intervention

At the first visit the participants will complete a hearing test using standard audiometry performed by the clinician and a screening using the IMD. The standard audiometry is used as a base test for the inclusion/exclusion criteria and as a control measure for the screening results of the IMD. The hearing devices will be programmed using both the RMD and the IMD during the course of the trial. The screening results from the IMD will be used for both fittings to ensure that the acoustic output of both methods is the same. The difference in the fitting process of the RMD and the IMD is the focus of the trial and not the actual output of the hearing aid.

The IMD will present tones from 250 Hz to 8000 Hz, and the participants will indicate when they've heard the tone. The tones are directed into the ears of the participants with supra-aural headphones. The test should take no more than 15 minutes. Depending on the randomization assignment, some participants will then start the fitting portion of the IMD. Hearing instruments will be connected using a wireless neck loop that the subjects will wear. Once the fitting has been programmed into the hearing aids the investigator will place the hearing aids in the subject's ears. The fitting process should not take more than 20 minutes. They will wear the programmed devices for approximately 10 hours per day for an overall time of approximately 20 +/-10 days for the trial. There are no surgical techniques used in the application of this device. It is a non-invasive device.

The study procedure will use a cross over design with two groups. One group will wear the hearing aids fitted with the IMD and one will wear the hearing aids fitting with the RMD. After 10 days they will switch to whichever method they did not have previously. As stated, the device is non-invasive and requires no surgical procedure. The device sound port will be inserted into the ear and the body of the device placed behind the ear each morning by the subjects themselves and removed each night by the subjects themselves. There is minimal training needed for a first time user to learn how to insert a hearing device. The subjects will be given an Instructions for Use booklet that explains how to insert the device and provides further instructions concerning cleaning, battery changing, and warnings.

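### Standard audiometry always precedes the IMD screening at visit 1, so test order cannot be separated from method in the secondary threshold comparison (research question 2)

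*Protocol*

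**What the plan says.** Protocol 9.3.1 describes visit 1 as a single sequence. After consent, history and otoscopy, "The initial hearing test is performed to determine hearing loss including air and bone audiometry". Next, "Inclusion/exclusion criteria will be determined". The Gothenburg questionnaire follows, and only then "They will complete a hearing screening using the IMD". The fitting comes last.

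The footnote to the study schedule confirms that this does not depend on the randomised group: "Everyone will use the IMD at the first visit to perform audiometry". Protocol 9.2.2 makes the pair of tests a secondary outcome: "The results from this screening will be compared with a standard audiometry test performed by the investigator". It places the comparison at the first visit. Protocol 8.2.1 gives the role of the manual test: "The standard audiometry is used as a base test for the inclusion/exclusion criteria and as a control measure".

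Randomisation covers other things. Protocol 6.2.1 allocates which fitting is worn first. The synopsis and 6.1 extend a randomised order to the laboratory speech testing. Protocol 7.3 describes a two-level test order by investigator and gives the reason: "This will minimize the bias created when one test condition is tested in the first or last position all of the time". None of these sections mentions the order of the two hearing tests.

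Two analyses of thresholds are named: a paired t-test (Protocol 11.4, SAP 4.1) and a nested model for ear, participant and investigator (Protocol 5.2 and 11.4.3, SAP 2.2.1). Neither has an order term.

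**The concern.** Research question 2 asks whether self-administered audiometry is equivalent to the clinical procedure. Each participant takes each test once, and the automated test is always second. A listener may do better on the second test through practice, or worse through fatigue. Either change would look exactly like a difference between methods. If it had the opposite sign to a true difference, it would hide that difference.

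This comparison matters because both fittings are calculated from the IMD thresholds (Protocol 8.1.2). It is the trial's only check of those thresholds against the clinical standard before release. Protocol 7.3 already states the principle that a condition should not always occupy the same position; it is not applied here.

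**Working it through.** **The plan's own figures.** The documents give no sample size, power or equivalence margin for research question 2. The only power in Protocol 11.2 (0.82) is for the three-category preference test. It reproduces: noncentrality 24 × 0.65² = 10.14 on 2 degrees of freedom gives 0.821. It has no bearing on thresholds.

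**Identifiability.** Write m for the true IMD-minus-standard difference and o for the change from first to second test. With the planned order every participant's difference has expectation m + o. A design matrix with intercept, method and order has rank 2 for 3 parameters, so m and o cannot be estimated separately at any sample size. If half the participants take the IMD test first, their expectation is m − o, the rank is 3, and the mean of the two groups is [(m + o) + (m − o)]/2 = m.

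**Inputs for size.**
- SD of the between-method difference: 6.4 dB (Protocol 3.4, from a cited study). It may not equal the SD of the quantity analysed.
- n = 24 minimum (Protocol 11.2), 40 maximum (synopsis).
- Order effect: not in the documents. I assume 1 to 2 dB, and show 3 and 5 dB for range.

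**Precision.** SE = 6.4/√n.
- n = 24: 6.4/√24 = 1.31 dB; half-width 2.069 × 1.306 = 2.70 dB.
- n = 40: 6.4/√40 = 1.01 dB; half-width 2.05 dB.

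A shift of 1 to 2 dB is therefore 1/2.70 = 37% to 2/2.70 = 74% of the half-width at n = 24.

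**False rejection when m = 0** (two-sided paired t-test at 5%, noncentral t with noncentrality o/SE):

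| Assumed order effect | n = 24 | n = 40 |
|---|---|---|
| 0 dB | 5% | 5% |
| 1 dB | 11% | 16% |
| 2 dB | 31% | 49% |
| 3 dB | 60% | 82% |
| 5 dB | 96% | 99.8% |

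More participants make this worse, because the bias stays constant while the SE shrinks.

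**After counterbalancing.** In 100,000 simulated trials with 12 participants per order and an order term, the bias was about 0 dB and false rejection 4.9% to 5.0% for order effects of 1 to 5 dB. If order were balanced but not modelled, the SD would rise only to √(6.4² + 1²) = 6.48 dB or √(6.4² + 2²) = 6.71 dB.

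**Limit of the remedy.** If the change is o₁ when the manual test comes first and o₂ when the automated test comes first, the mean of the two groups is m + (o₁ − o₂)/2. Counterbalancing removes the order effect only as far as o₁ and o₂ are alike.

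**The case against.** There is a fair case for the present order. The manual audiogram decides eligibility, so doing it first spares ineligible people a test with software that has no CE mark. It also means that the examiner-dependent test is recorded before any IMD result exists, which protects it from expectation. The comparison is secondary in a trial described as exploratory. An assumed 1 to 2 dB lies inside the 5 dB test-retest difference that Protocol 3.4 calls acceptable. Practice and fatigue act in opposite directions.

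Much of this stands, and it limits the weight of the point. It does not restore identifiability. Protocol 8.2.1 makes the standard audiogram the basis for eligibility, but does not say that it must come before the screening. The screening is non-invasive, limited to 80 dB and takes at most 15 minutes.

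Three stronger readings are tempting and not supported:

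- **Untrained listeners, hence a large practice effect.** Participants have never worn hearing aids, and Protocol 3.8 speaks of an initial hearing test. But the recruitment database in Protocol 7.2 includes people who have already been tested.
- **Fatigue after a long visit.** Protocol 6.1 caps clinic time for laboratory tests at 1.5 hours, and a questionnaire separates the two hearing tests. Fatigue is possible but not shown.
- **A bias many times the expected difference.** The 0.1 dB in SAP 2.2.1 averages values running from −3 to 3.6 dB across frequencies. A ratio to a near-zero mean says little; the half-width is the better yardstick.

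**Conclusion.** The concern holds for research question 2. With one fixed order, one measurement per method and no retest, order and method are completely aliased, and neither planned analysis can separate them. This follows from the design and rests on no assumption.

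The size does rest on assumptions. An order effect of 1 to 2 dB, with an SD of 6.4 dB, raises false rejection from 5% to about 11% to 31% at n = 24. The true size and direction are unknown. Because no equivalence margin is stated, the risk of wrongly declaring equivalence cannot be calculated.

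A reader might infer that the primary outcome is compromised too. It is not: both fittings use the same IMD screening results, so the order of the hearing tests does not confound the questionnaire comparison. The change should be made, but the trial's main question does not depend on it.

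**What to change.** 1. After consent, history and otoscopy, randomise which hearing test comes first, 1:1 within investigator. Use a short list separate from the fitting-sequence list, so that people later found ineligible do not use up its blocks.
2. Keep eligibility based on the standard audiogram, and decide it once both tests are done.
3. Do not open the IMD result until the standard audiogram is recorded.
4. Analyse threshold differences in the planned nested model with a test-order term, in place of the plain paired t-test. State that this assumes similar carry-over in both directions.

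**Cost.** About half of those later found ineligible will have done a screening of up to 15 minutes with the non-CE-marked software before eligibility is confirmed. Withholding the result screen needs a site instruction, because Protocol 3.2 has a consultant guide the user and help explain the screening results. Otherwise the cost is one short list and one model term.

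If the sponsor keeps the fixed order, the protocol and report should state the limitation, and the threshold difference, or its absence, must not be attributed to method alone.
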